**Table 2: Study Endpoints (Continued)**

Endpoint	Name	Description
Secondary	Cytogenetic response	Proportion of subjects achieving complete cytogenetic response or partial cytogenetic response according to IWG 2006 response criteria ( Appendix D ).
Secondary	Progression-free survival (PFS)	Time from randomization to the first documented PD or death due to any cause, whichever occurs first.
Secondary	Duration of response	Duration of hematologic response/improvement is defined as the time from the date response/improvement is first observed until the date the subject has a subsequently documented relapse or disease progression as defined by the IWG 2006 response criteria ( Appendix D )
Secondary	Time to AML transformation	Time from randomization to AML transformation.
Secondary	Transformation to AML	Proportion of subjects with disease transformation to AML.
AML Cohort		
Primary	Overall response rate	Proportion of AML subjects achieving an overall response (CR or CRi) based on modified IWG 2003 response criteria for AML ( Appendix K ).
Secondary	Time to response	Time from randomization to first documented response based on modified IWG 2003 response criteria for AML ( Appendix K ).
Secondary	Relapse-free survival	Relapse-free survival is defined only for subjects who achieve CR or CRi and is measured as the interval from the date of first documented CR or CRi to the date of documented relapse, death from any cause, or lost to follow-up, whichever occurs first ( Appendix K ).
Secondary	Complete cytogenetic response (CyCR)	Proportion of subjects with complete cytogenetic response (CyCR) based on modified IWG 2003 response criteria for AML ( Appendix K ).
Secondary	Hematologic Improvement Rate	Rate of HI-NE + HI-P + HI-E according to IWG 2006 response criteria ( Appendix D ).
Secondary	Duration of response	Duration of response is defined as the time from the first documented CR/CRi to documented morphologic relapse, PD based on modified IWG 2003 response criteria for AML ( Appendix K ), or death due to any cause, whichever occurs first.
Phase 2: Both Cohorts		
Secondary	Safety	Type, frequency, seriousness and severity of adverse events (AEs), and relationship of AEs to study treatment, clinical laboratory evaluations.

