The End of Trial is defined as either the date of the last subject last visit for the completion of post-treatment follow-up, or the date of receipt of the last data point from the last subject that is required for primary, secondary and/or exploratory analyses, whichever is the later date. See Section 3.3 of the protocol.

Study Treatments

Subjects will be randomized 1:1 to receive either:

Treatment Arm A: Subcutaneous azacitidine (75 mg/m² daily for 7 days every 4 weeks [Q4W]) in combination with intravenous (IV) durvalumab at a dose of 1500 mg on Day 1 Q4W,

Or

Treatment Arm B: Subcutaneous azacitidine alone at the dose of 75 mg/m² daily for 7 days Q4W.

Table 2: Study Endpoints

Endpoint	Name	Description
MDS Cohort		
Primary	Overall response rate	Proportion of MDS subjects achieving an overall response (CR, mCR, PR or HI), based on IWG 2006 response criteria (Appendix 17.2).
Secondary	Time to response	Time from randomization to first documented response according to IWG 2006 response criteria (Appendix 17.2).
	Relapse-free survival	Time from the date CR or PR is first documented until the date of documented relapse, death from any cause, or lost to follow-up, whichever occurs first according to IWG 2006 response criteria (Appendix 17.2).
	Cytogenetic response (CyCR)	Proportion of subjects achieving complete cytogenetic response or partial cytogenetic response according to IWG 2006 response criteria (Appendix 17.2).
	Progression-free survival (PFS)	Time from randomization to the first documented PD, relapse or death due to any cause, whichever occurs first.
	Duration of response	Duration of response is defined as the time from first response observed (CR, mCR, PR or HI) until relapse, PD or death as defined by the IWG 2006 criteria (Appendix 17.2).
	Time to AML transformation	Time from randomization to AML transformation defined by at least 30% of myeloblasts either in the bone marrow or the peripheral blood.
	Transformation to AML	Proportion of subjects with disease transformation to AML.
AML Cohort		
Primary	Overall response rate	Proportion of AML subjects achieving an overall response (CR or CRi) based on modified IWG 2003 response criteria for AML. (Appendix 17.3).
Secondary	Time to response	Time from randomization to first documented response based on modified IWG 2003 response criteria for AML (Appendix 17.3).

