Duration of response will be calculated only for subjects who achieve CR, mCR, PR or HI for the MDS Cohort, CR or CRi for the AML Cohort. Duration of response is defined as the time from first response observed until relapse, PD or death. Duration of response will be censored at the last response assessment date that the subject is known to be progression-free for:

- Subjects who have not relapsed, progressed or died at the time of analysis.
- Subjects who have withdrawn consent or are lost to follow-up prior to documentation of progression.

Censoring rules are defined in [Table 4](#).

Duration of response will be analyzed using the KM method. Median duration of response along with two-sided 95% CI will be provided for each cohort and treatment group.

In addition, the duration of each specific subcategory of response in the MDS Cohort (CR, mCR, PR or HI) and in the AML Cohort (CR) will be summarized using standard descriptive statistics.

Relapse-free Survival (RFS)

Relapse-free survival is defined only for subjects who achieve CR or PR for MDS subjects, CR and CRi for AML subjects, and is measured as the interval from the date of first documented response to the date of disease relapse or death from any cause, whichever occurs first. Subjects who are still alive and relapse-free will be censored at the date of their last response assessment. The RFS curve will be estimated using KM method.

Median RFS along with two-sided 95% CI will be provided for each cohort and treatment group. The RFS at 6 and 12 months will be estimated and compared using Kaplan-Meier (KM) method.

Censoring rules are defined in [Table 4](#).

Cytogenetic Response

External central pathology/cytogenetic reviewers will review the morphologic/cytogenetic data from bone marrow aspirate (BMA), bone marrow biopsies (if performed) to determine whether a subject achieved a cytogenetic response (complete or partial cytogenetic responses for MDS subjects and cytogenetic complete response for AML subjects). For cytogenetic response evaluable subjects (ie subjects with baseline cytogenetic abnormalities), the number and percentage of subjects who achieve the cytogenetic responses will be summarized together with associated two-sided 95% CI.

MDS Cohort:

Progression-free Survival (PFS)

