Progression-free survival is calculated as the time from randomization to the first documented progression, relapse or death due to any cause during or after the treatment period, whichever occurs first. Subjects who are still alive and progression-free will be censored at the date of their last response assessment. The PFS curve will be estimated using KM method.

Median PFS along with two-sided 95% CI will be provided for each cohort and treatment group. The PFS at 6 and 12 months will be estimated and compared using Kaplan-Meier (KM) method.

A sensitivity analysis of PFS will be performed, censoring PFS at the time of subsequent systemic anticancer therapy if the subject did not progress before that time.

Transformation to AML and Time to AML Transformation

Number of subjects with transformation to AML and time to transformation to AML will be summarized. Time to transformation to AML is defined as the time from the date of randomization until the date the subject has documented transformation to AML (at least 30% of BM blats). Subjects who do not transform to AML will be censored at the date last disease assessment date. Median time to transformation to AML and associated two-sided 95% CI will be estimated using KM method.

AML Cohort:

HI

Rate of HI – erythroid response (HI-E), hematological improvement – platelet response (HI-P) and hematological improvement – neutrophil response (HI-N) according to IWG 2006 response criteria for MDS ([Appendix 17.2](#)), will be provided together with Wald asymptotic two-sided 95% CIs.

Table 4: Event and Censoring Rules for Progression-free Survival, Duration of Response, Time-to-Response and Relapse-free Survival

Situation	Date of Progression or Censoring	Situation Outcome
Censoring Rules for PFS and DoR		
Progression	If the first PD is a scheduled assessment then Date of first PD; If the first PD is an unscheduled assessment and no previous assessment, then Date of PD; If the first PD is an unscheduled assessment and has previous assessment, then Date of previous assessment (regardless of the response type).	Event
Death between scheduled assessments or within the first two missed scheduled assessments	Date of death	Event
No progression	Date of last adequate assessment with evidence of no PD	Censored
Death or progression after two or more missed scheduled assessments	Date of last adequate assessment with evidence of no PD; if no adequate assessment exists then censored at date of first dose	Censored

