Disease Progression (PD)	
 ▪ If condition for Transformation to AML and relapse after CR/PR are not verified ▪ For patients with: 
 ▪ Nadir value less than 5% blasts: $\geq 50\%$ increase in blasts to $> 5\%$ blasts ▪ Nadir value 5% - 10% blasts: $\geq 50\%$ increase in blasts to $> 10\%$ blasts ▪ Nadir value 10% - 20% blasts: $\geq 50\%$ increase in blasts to $> 20\%$ blasts 
AND ANY OF THE FOLLOWING
 
 ▪ $\geq 50\%$ decrement from max level of ANC and ANC < 1.0 GI/L 
OR
 
 ▪ $\geq 50\%$ decrement from max level of Platelets and Platelets < 100 GI/L 
OR
 
 ▪ Reduction from max level of Hgb ≥ 20 g/L and Hgb < 110 g/L 
OR
 
 • Transfusion dependence (apply to baseline TI subjects only)

^a Dysplastic changes should consider the normal range of dysplastic changes (modification).

Source: Cheson BD, Greenberg PL, Bennett JM, Lowenberg B, Wijermans PW, Nimer SD, et al. Clinical application and proposal for modification of the International Working Group (IWG) response criteria in myelodysplasia. Blood. 2006; 108(2): 419-25.

Altering Disease Natural History	
Disease transformation	Transformation to AML (30% or more blasts)
Relapse after CR or PR	
 • BM % blast \geq baseline % blast and BM % blast \geq 5% 
OR
 
 • \geq 50% decrement from max level of ANC and ANC < 1.0 GI/L 
OR
 
 • \geq 50% decrement from max level of Platelets and Platelets < 100 GI/L 
OR
 
 • Reduction from max level of Hgb \geq 20 g/L and Hgb < 110 g/L 
OR
 
 • RBC/platelet transfusion is given after CR/PR

Cytogenetic Response	
Complete	Disappearance of the chromosomal abnormality without appearance of new ones
Partial	At least 50% reduction of the chromosomal abnormality

Hematological Improvement (HI)	

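### SAP Table 4 has no relapse event for PFS or DoR, although SAP 10.2 counts relapse; in MDS, SAP 17.2 keeps relapse after CR/PR and AML transformation out of PD, so literal programming would miss both

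*SAP*

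**What the plan says.** **PFS (MDS cohort only).** Protocol Table 2 defines it as "Time from randomization to the first documented PD or death due to any cause, whichever occurs first". SAP Table 2 adds relapse: "Time from randomization to the first documented PD, relapse or death due to any cause, whichever occurs first". SAP 10.2 does the same: "time from randomization to the first documented progression, relapse or death due to any cause during or after the treatment period".

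**DoR (both cohorts).** SAP 10.2 states: "Duration of response is defined as the time from first response observed until relapse, PD or death". Its text censors two groups: "Subjects who have not relapsed, progressed or died at the time of analysis", and those who withdraw consent or are lost before progression is documented. It then sends the reader to Table 4 for the censoring rules.

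**SAP Table 4, block for PFS and DoR.** There are four rows:
- progression, dated from the first PD: event;
- death between visits or within the first two missed visits: event;
- no progression: censored at "Date of last adequate assessment with evidence of no PD";
- death or progression after two or more missed visits: censored.

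Relapse has an event row only in the separate RFS block.

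**SAP 17.2, MDS definition of PD.** It opens with a precondition: "If condition for Transformation to AML and relapse after CR/PR are not verified".

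**The concern.** The definitions in the text and the table that implements them give different event lists for the same endpoints. One might expect the word progression in Table 4 to cover relapse. Two things stand against that: Table 4 treats relapse as a separate situation in its RFS block, and SAP 17.2 makes PD and relapse after CR/PR mutually exclusive in MDS.

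The same MDS subject who relapses from CR is then an event under SAP 10.2 and censored under Table 4. Two programmers could each follow the SAP and produce different PFS and DoR curves. If SAP 10.2 is taken to prevail, there is still no rule for dating a relapse in these two endpoints, because the scheduled/unscheduled dating rule in the PFS/DoR block refers to PD alone.

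DoR also has a use beyond secondary reporting. Protocol 9.3.1 and 9.3.2 and SAP 4.3.1 and 4.3.2 name it as the example of a secondary endpoint whose difference can let a cohort continue at the futility look.

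**Working it through.** No sample size, power or alpha figure depends on this point, so there is no planned figure to reproduce. The check is a comparison of rules, then a size under stated assumptions.

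**1. MDS: can a CR/PR responder ever be PD?** SAP 17.2 requires for PD a blast rise from nadir and at least one of four further conditions. Each of the four also meets a relapse criterion after CR/PR:

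| Further condition for PD | Relapse after CR/PR |
|---|---|
| ANC down by at least 50% from maximum and below 1.0 | same criterion |
| Platelets down by at least 50% from maximum and below 100 | same criterion |
| Hgb down by at least 20 g/L from maximum and below 110 g/L | same criterion |
| Transfusion dependence (baseline-independent subjects) | any RBC or platelet transfusion after CR/PR |

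After CR/PR, whatever would satisfy PD satisfies relapse first, and relapse blocks PD. Coding these rules over a grid of 3 × 4 × 6 × 2 × 2 × 2 × 2 = 1152 post-CR/PR profiles (baseline, nadir and current blasts, ANC, platelets, Hgb, transfusion) gave PD in 0 of 1152.

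Worked case: baseline blasts 12%, nadir 3%, now 14%; ANC 0.4 from 2; platelets 40 from 150; Hgb 9 from 12 g/dL. The blast rule for PD is met (14 ≥ 1.5 × 3 = 4.5, and above 5%), and so are the cytopenia conditions. With a prior CR/PR the result is relapse, not PD. Without one, the same values are PD.

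**2. MDS: transformation.** The same precondition withholds PD when transformation (30% or more blasts) is met. The best-response ranking in SAP 10.1 also lists PD and disease transformation separately. Neither Table 4 nor the SAP 10.2 event text for PFS or DoR names transformation.

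**3. MDS responders with mCR or HI only.** The SAP 17.2 relapse category covers CR and PR only, so these subjects can still have PD.

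**4. AML (DoR only).** SAP 17.3 has no such exclusion. CR and CRi need marrow blasts below 5%, and marrow relapse needs more than 15%. The rise exceeds (15 − 5)/5 = 200%, above the 50% that PD needs. (The 50% is read as relative, since only the separate 10% rule is marked absolute.) Marrow relapse is therefore also PD. Relapse on more than 5% blood blasts alone is not, because the blood-blast route to PD applies only when the lowest marrow value is above 70%.

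**5. Size if relapse is censored.** The documents give no relapse rate, so the share s of first events that are relapses is an assumption. With constant hazards and total hazard λ, the median is ln 2/λ. With relapse censored it becomes ln 2/[λ(1 − s)], so the factor is 1/(1 − s):

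- s = 20%: 1/0.8 = 1.25
- s = 40%: 1/0.6 = 1.67
- s = 60%: 1/0.4 = 2.50

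**6. Allowing for deaths after relapse.** Table 4 still counts a death within the first two missed visits. As an illustration, take CR/PR responders with relapse median 12 months and deaths without relapse at 20% of events. The total hazard is (ln 2/12)/0.8 = 0.0722 per month.

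- Relapse counted: 12-month rate exp(−12 × 0.0722) = 42%.
- Every relapse censored, no later death counted: exp(−12 × 0.2 × 0.0722) = 84%.
- Deaths within 3 to 6 months of relapse counted, with assumed median survival after relapse of 4 to 12 months (simulation, 12 to 27 months of follow-up less 4.5 months to response): 58% to 76%.

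**The case against.** The strongest reply is that the SAP does not decide to censor relapses. SAP Table 2 and the SAP 10.2 text count them, the DoR text censors only subjects without relapse, and the PFS text does not cite Table 4, although the table's title covers PFS. A reader might infer that relapsing responders will be censored. The documents support only a contradiction, which leads to censoring if the table is followed literally. That part of the reply stands.

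Three further limits stand.

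- **Size.** A reader might infer that nearly all DoR events disappear. That is the extreme case: it needs an assumed high relapse share and ignores the later deaths that Table 4 counts (step 6). It also describes CR/PR responders only, whereas MDS DoR includes mCR and HI responders, which dilutes the effect on the planned curve.
- **Cohort.** A reader might carry the MDS exclusivity over to AML. SAP 17.3 does not contain it.
- **Direction between arms.** A reader might infer that the arm with more CR/PR is favoured. For PFS the inflation does grow with the share of subjects in CR/PR. For DoR, computed among responders, it depends on the CR/PR share of responders, about which the documents say nothing by arm.

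It is also fair that RFS has proper relapse rows and covers MDS CR/PR and AML CR/CRi, so these relapses will be reported there. That does not repair PFS or DoR, and it does not cover transformation.

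**Conclusion.** The point holds as an internal contradiction on two secondary endpoints, and one of its two readings gives a wrong result. Programmed literally, Table 4 does not count an MDS relapse after CR/PR, or a transformation to AML, as a PFS or DoR event. The subject is censored, or becomes a late event if a death that Table 4 still counts follows. In AML the loss is mainly relapse on blood blasts alone.

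Under constant hazards the median is inflated by 1.25 to 2.5 for assumed relapse shares of 20% to 60%, and by less when deaths soon after relapse are counted. These shares are assumptions. The primary ORR test and the sample size are untouched. The only link to a trial decision is through DoR as an example in the third futility condition.

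Separately, the protocol's PFS is PD or death, and SAP Section 15 does not list the addition of relapse as a change.

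**What to change.** In SAP Table 4, in the block for PFS and DoR:

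1. Change the event row to progression, relapse or transformation to AML (MDS), dated at the first of these, with the same scheduled/unscheduled dating rule.
2. Change the no-progression row to no progression, relapse or transformation, censored at the last adequate assessment without any of them.
3. Align the row on death or progression after two or more missed scheduled assessments in the same way.

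Add transformation to the PFS and DoR event text in SAP 10.2, with the SAP Table 2 entries to match. List in SAP Section 15 that relapse and transformation are added to the protocol's PFS definition of PD or death.

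The cost is three table rows, a few words in the endpoint definitions and one line in Section 15. No new data are needed, because relapse is already derived for RFS and transformation is already an endpoint.

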Censoring Rules for RFS		
Relapse	If the first relapse is a scheduled assessment then Date of first relapse; If the first relapse is an unscheduled assessment and no previous assessment, then Date of relapse; If the first relapse is an unscheduled assessment and has previous assessment, then Date of previous assessment (regardless of the response type).	Event
Death between scheduled assessments or within the first two missed scheduled assessments	Date of death	Event
No relapse	Date of last adequate assessment with evidence of no relapse	Censored
Death or progression after two or more missed scheduled assessments	Date of last adequate assessment with evidence of no relapse; if no adequate assessment exists then censored at date of first dose	Censored
Censoring Rules for PFS (sensitivity analysis), DoR and RFS		
Additional therapy received prior to progression or death	Date of additional systemic anticancer therapy	Censored

Censoring Rules for TTR		
Subject responded before PD	First documented response date (CR, PR, mCr, or HI for mDS Cohort, CR or CRi for AML Cohort)	Event
Subject responded after PD	Date of last adequate disease assessment at PD date or death date	Censored
Other case	Date of last adequate disease assessment; if no adequate assessment exists, then censored at date of first dose	Censored

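### SAP Table 4 censors DoR, RFS and sensitivity PFS at the start of new therapy rather than at the last adequate assessment, so sparsely assessed time after treatment counts as event-free

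*SAP*

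**What the plan says.** SAP 10.2, Table 4, has a block headed "Censoring Rules for PFS (sensitivity analysis), DoR and RFS". Its single row covers a subject who receives further therapy before progression or death. The censoring date is the "Date of additional systemic anticancer therapy".

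The neighbouring rows use a different clock:
- No progression (PFS, DoR): "Date of last adequate assessment with evidence of no PD".
- No relapse (RFS): "Date of last adequate assessment with evidence of no relapse".
- "Death or progression after two or more missed scheduled assessments": censored back at the last adequate assessment, or at first dose if there is none.

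The text of SAP 10.2 follows the neighbouring rows for two of the three endpoints. For DoR: "Duration of response will be censored at the last response assessment date that the subject is known to be progression-free for" subjects without an event and those who withdraw or are lost. For RFS: "Subjects who are still alive and relapse-free will be censored at the date of their last response assessment". Neither passage mentions new therapy, but both refer the reader to Table 4. For the PFS sensitivity analysis the text agrees with the new-therapy row: "censoring PFS at the time of subsequent systemic anticancer therapy if the subject did not progress before that time".

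**The concern.** A censoring date says how long a subject is known to have been free of the event. For relapse and progression that knowledge comes from disease assessments. Starting a new drug is not an assessment.

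Under Table 4, a responder who stops study treatment without progression and later starts another therapy is credited with the whole interval up to that start. An otherwise identical responder who starts nothing is credited only to the last assessment. The subject who needed further treatment can therefore show the longer response.

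At stake are the DoR and RFS curves and medians in both cohorts, the sensitivity PFS in the MDS cohort, and the stratified log-rank comparisons of these endpoints. Censoring because of new therapy is not in dispute; only the date is.

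**Working it through.** **1. What is observed after treatment stops**

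| Source | What is collected | Until when |
|---|---|---|
| Protocol Table 3, 6.7.1, 6.7.3 | Marrow and IWG response | Every 3 cycles (84 days) and at treatment discontinuation; nothing scheduled later |
| Protocol 6.6.6.1 | Haematology, including percent blasts | 28-day visit; also 90-day visit for durvalumab subjects |
| Protocol 6.7.6 | Transfusions | 90 days after last dose, or the discontinuation visit if later |
| Protocol 6.7.7 | Determination of progression | Recorded, with no scheduled assessment behind it |
| Protocol 3.2.3.2, 6.15 | Survival, later therapy, AML transformation | Telephone every 3 months |

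The start of new therapy is thus collected over a period in which relapse is only partly observed, and after about 90 days hardly at all.

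**2. One pair of responders (illustrative days)**

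Both have first response on Day 85 and last adequate assessment on Day 170. One starts new therapy on Day 260.
- New therapy: 260 − 85 = 175 days credited.
- No new therapy: 170 − 85 = 85 days credited.
- Difference: 90 days, all of it after the last assessment.

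**3. Date imputation**

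SAP 17.1.5 moves a partial subsequent-therapy date to the end of the month or to 31 December. The censoring date can then be up to 30 days late (day missing) or 364 days late (day and month missing).

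**4. Possible size**

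The plan states no figure to reproduce, and every input here is an assumption. Take exponential relapse with median 10 months (hazard λ = ln 2/10 = 0.0693) and exponential departure from assessment without relapse with mean 12 months (hazard 1/12 = 0.0833).
- Proportion leaving without relapse: f = 0.0833/(0.0693 + 0.0833) = 0.546.
- Assessed time per responder: 1/(0.0693 + 0.0833) = 6.55 months.
- A fraction p of leavers starts new therapy after a mean gap of g months. Extra credited time is f × p × g, and the event rate is too low by extra/(6.55 + extra).

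| p, g | Extra (months) | Rate too low by | Simulated KM median: Table 4 v last assessment |
|---|---|---|---|
| 20%, 2 | 0.218 | 0.218/6.77 = 3% | 10.3 v 10.0 |
| 40%, 4 | 0.873 | 0.873/7.42 = 12% | 11.3 v 10.0 |
| 60%, 6 | 1.965 | 1.965/8.52 = 23% | 12.8 v 10.0 |

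These rows assume that no relapse is detected after departure. Now let relapse be detectable for w months. The extra becomes f·p·g·exp(−w/g)·exp(−λw), and assessed time rises by f·[p(1 − exp(−(λ + 1/g)w))/(λ + 1/g) + (1 − p)(1 − exp(−λw))/λ].
- Middle row, w = 1: 0.635/(7.05 + 0.635) = 8%.
- Middle row, w = 3: 0.335/(7.86 + 0.335) = 4%; median about 10.3 to 10.4 v 10.0.
- Heaviest row, w = 1: 1.552/(7.05 + 1.552) = 18%; simulated median 11.9 v 10.0.

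**5. Second model**

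This one has 84-day assessments, a data cut at 24 months, true median 6 or 12 months, 20% or 40% of responders leaving without relapse and all of those later starting therapy, mean gap 1, 3 or 6 months, and no detection in follow-up. With the discontinuation assessment done, Table 4 raises the 12-month event-free estimate by 0.5 to 13.6 points (0.526 v 0.521 at the low end, 0.383 v 0.247 at the high end). Without that assessment the range is 0.5 to 15.7 points. The median moves by either nothing or 2.8 months, which is one assessment interval (84/30.4375 = 2.76), so the 12-month estimate is the better guide.

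**The case against.** The strongest reply is that follow-up is not blind. In SAP 17.3, AML relapse can be met by blood blasts alone. In SAP 17.2, MDS relapse after CR or PR can be met by a fall in counts or by a transfusion. Haematology and transfusion records continue for one to three months, progression can be reported later, and deaths, which are events for these endpoints, are followed throughout. A reader might infer from the schedule that relapse cannot be documented at all once treatment stops; the documents do not support that. The reply stands for the early part of the gap and shrinks the effect, as the detection rows in the working show. It does not cover later time, and it gives no reason to prefer the therapy date.

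Second, the text sends the reader to Table 4, so the table may be read as supplying a special case. That is fair. Still, the RFS sentence, read as written, also fits an event-free subject on new therapy and gives a different date. For sensitivity PFS, text and table agree, so there the point is a weak choice of date and not a contradiction.

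Third, reach is limited. ORR and main-analysis PFS do not use this row. A reader might infer that the futility decision is compromised, since DoR is named there. It is only an example within the third of three alternative conditions, and termination is discretionary. A reader might also infer a bias towards one arm. Later therapy could differ by arm in an open-label trial, and the 90-day haematology applies only to durvalumab subjects, but nothing in the documents fixes a direction.

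**Conclusion.** The point holds as a defect in the censoring date for DoR, RFS and sensitivity PFS. The row departs from the other non-event rows of Table 4 and credits time with little or no assessment as event-free, so these estimates tend to be too long.

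The size cannot be read from the documents, which give no gap lengths, no use of later therapy and no rate of stopping without relapse. It is negligible if new therapy follows the discontinuation assessment promptly. In the assumed scenarios it exceeds a month on the median only with long gaps and little or no detection in follow-up. A flat statement that the medians are materially too long is therefore not supported.

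Table 4 also does not say which row applies when new therapy follows two or more missed assessments. A later death or progression would be censored back to the last assessment, while the therapy would be censored forward at its start.

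**What to change.** - Reword the additional-therapy row so that the date is the last adequate assessment showing no PD (no relapse, for RFS) on or before the day additional systemic anticancer therapy starts; where no adequate assessment exists, the first-dose date; outcome censored. Sensitivity PFS needs that fallback.
- State which row governs when this row and the two-missed-assessments row both fit.
- Align the PFS sensitivity sentence and the DoR and RFS paragraphs in SAP 10.2 with the new row.

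The cost is SAP wording and programming from dates already collected; no new data are needed. The downside is that estimates become slightly shorter.
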